### **9.2 Study completion and post-study treatment**

Study completion is defined as when the last subject finishes their Study Completion visit (Week 40), and any repeat assessments associated with this visit have been documented and

followed-up appropriately by the Investigator, or in the event of an early study termination decision, the date of that decision.

A subject will be considered to have completed the study if he/she received a maximum of 30 weeks of study treatment and upon completion of the scheduled study assessments and procedures up to and including visit Week 40.

The investigator must provide follow-up medical care for all subjects from the study, or must refer them for appropriate ongoing care.

## **10 Safety monitoring and reporting**

### **10.1 Definition of adverse events and reporting requirements**

#### **10.1.1 Adverse events**

An adverse event (AE) is any untoward medical occurrence (e.g., any unfavorable and unintended sign [including abnormal laboratory findings], symptom or disease) in a subject or clinical investigation subject after providing written informed consent for participation in the study. Therefore, an AE may or may not be temporally or causally associated with the use of a medicinal (investigational) product.

In addition, all reports of intentional misuse and abuse of the product are also considered an adverse event irrespective of whether a clinical event has occurred.

The investigator has the responsibility for managing the safety of individual subject and identifying adverse events.

Novartis qualified medical personnel will be readily available to advise on trial related medical questions or problems.

The occurrence of adverse events must be sought by non-directive questioning of the subject at each visit during the study. Adverse events also may be detected when they are volunteered by the subject during or between visits or through physical examination findings, laboratory test findings, or other assessments.

Adverse events must be recorded in the Adverse Events eCRF under the signs, symptoms or diagnosis associated with them, accompanied by the following information (as far as possible) (if the event is serious refer to [Section 10.1.2](#)):

1. The severity grade.
  - mild: usually transient in nature and generally not interfering with normal activities
  - moderate: sufficiently discomforting to interfere with normal activities
  - severe: prevents normal activities
2. Its relationship to the study treatment (suspected: Yes/No). If the event is due to lack of efficacy or progression of underlying illness (i.e. progression of the study indication), the assessment of causality will usually be 'Not suspected'. The rationale for this guidance is that the symptoms of a lack of efficacy or progression of underlying illness are not caused by the trial drug, they happen in spite of its administration and/or both lack of efficacy and progression

of underlying disease can only be evaluated meaningfully by an analysis of cohorts, not on a single subject.

3. Its duration (start and end dates) or if the event is ongoing, an outcome of not recovered/not resolved must be reported.

4. Whether it constitutes a serious adverse event (SAE - see [Section 10.1.2](#) for definition of SAE) and which seriousness criteria have been met.

5. Action taken regarding with study treatment.

All adverse events must be treated appropriately. Treatment may include one or more of the following:

- dose not changed
- dose reduced/increased
- drug interrupted/withdrawn

6. Concomitant medication or non-drug therapy given

7. Its outcome: not recovered/not resolved, recovered/resolved, recovered/resolved with sequelae, fatal, unknown

Conditions that were already present at the time of informed consent should be recorded in medical history of the subject.

Adverse events (including lab abnormalities that constitute AEs) should be described using a diagnosis whenever possible, rather than individual underlying signs and symptoms.

Adverse event monitoring should be continued for at least 10 weeks following the last dose of study treatment.

Once an adverse event is detected, it must be followed until its resolution or until it is judged to be permanent (e.g. Continuing at the end of the study), and assessment must be made at each visit (or more frequently, if necessary) of any changes in severity, the suspected relationship to the interventions required to treat it, and the outcome.

**Worsening of lichen planus** in this study is evaluated via the use of efficacy assessments (e.g. IGA, REU, LPPAI, PSAD) and is **not** expected to be captured as an AE in the CRF capturing adverse events. Exceptions include cases when a new type of lichen planus is diagnosed, or the worsening is so severe that a qualitatively different status is reached.

Information about adverse drug reactions for the investigational drug can be found in the Investigator's Brochure (IB).

Abnormal laboratory values or test results constitute adverse events only if they fulfill at least one of the following criteria:

- they induce clinical signs or symptoms
- they are considered clinically significant
- they require therapy

Clinically significant abnormal laboratory values or test results must be identified through a review of values outside of normal ranges/clinically notable ranges, significant changes from baseline or the previous visit, or values, which are considered non-typical in subjects with the

underlying disease. Alert ranges for laboratory and other test abnormalities are included in [Section 15.1](#).

### 10.1.2 Serious adverse events

An SAE is defined as any adverse event [appearance of (or worsening of any pre-existing)] undesirable sign(s), symptom(s), or medical conditions(s) which meets any one of the following criteria:

- fatal
- life-threatening

Life-threatening in the context of a SAE refers to a reaction in which the subject was at risk of death at the time of the reaction; it does not refer to a reaction that hypothetically might have caused death if it were more severe (please refer to the ICH-E2D Guidelines).

- results in persistent or significant disability/incapacity
- constitutes a congenital anomaly/birth defect
- requires inpatient hospitalization or prolongation of existing hospitalization, unless hospitalization is for:
  - routine treatment or monitoring of the studied indication, not associated with any deterioration in condition
  - elective or pre-planned treatment for a pre-existing condition that is unrelated to the indication under study and has not worsened since signing the informed consent
  - social reasons and respite care in the absence of any deterioration in the subject's general condition
  - treatment on an emergency outpatient basis for an event not fulfilling any of the definitions of a SAE given above and not resulting in hospital admission
- is medically significant, e.g. defined as an event that jeopardizes the subject or may require medical or surgical intervention to prevent one of the outcomes listed above

Medical and scientific judgment should be exercised in deciding whether other situations should be considered serious reactions, such as important medical events that might not be immediately life threatening or result in death or hospitalization but might jeopardize the subject or might require intervention to prevent one of the other outcomes listed above. Such events should be considered as "medically significant." Examples of such events are intensive treatment in an emergency room or at home for allergic bronchospasm, blood dyscrasias, or convulsions that do not result in hospitalization or development of dependency or abuse (please refer to the ICH-E2D Guidelines).

All malignant neoplasms will be assessed as serious under "medically significant" if other seriousness criteria are not met and the malignant neoplasm is not a disease progression of the study indication.

Any suspected transmission via a medicinal product of an infectious agent is also considered a serious adverse reaction.

All reports of intentional misuse and abuse of the product are also considered serious adverse event irrespective if a clinical event has occurred.

### **10.1.3 SAE reporting**

To ensure subject safety, every SAE, regardless of causality, occurring after the subject has provided informed consent and until 30 days [after the last study visit (Week 40) must be reported to Novartis safety within 24 hours of learning of its occurrence. Detailed instructions regarding the submission process and requirements are to be found in the investigator folder provided to each site.

1. **Screen Failures** (e.g. a subject who is screened but is not treated or randomized): SAEs occurring after the subject has provided informed consent until the time the subject is deemed a Screen Failure must be reported to Novartis.
2. **Randomized OR Treated Subjects:** SAEs collected between time subject signs ICF until 10 weeks after the subject has discontinued or stopped study treatment

All follow-up information for the SAE including information on complications, progression of the initial SAE and recurrent episodes must be reported as follow-up to the original episode within 24 hours of the investigator receiving the follow-up information. An SAE occurring at a different time interval or otherwise considered completely unrelated to a previously reported one must be reported separately as a new event.

If the SAE is not previously documented in the Investigator's Brochure or Package Insert (new occurrence) and is thought to be related to the study treatment, a CMO & PS Department associate may urgently require further information from the investigator for health authority reporting. Novartis may need to issue an Investigator Notification (IN) to inform all investigators involved in any study with the same study treatment that this SAE has been reported.

Suspected Unexpected Serious Adverse Reactions (SUSARs) will be collected and reported to the competent authorities and relevant ethics committees in accordance with EU Guidance 2011/C 172/01 or as per national regulatory requirements in participating countries.

Any SAEs experienced after the 10-week period following the last administration of study treatment should only be reported to Novartis Safety if the investigator suspects a causal relationship to study treatment.

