#### **Treatment Period 1:**

Treatment Period 1 is placebo-controlled and covers the time from Week 0 (randomization visit) to Week 16. Patients who meet all eligibility criteria are randomized in a 2:1 ratio to one of the following two treatment arms **within** their cohort:

- **Secukinumab 300 mg every 4 weeks arm:** subjects receive a weekly induction treatment followed by secukinumab 300 mg every 4 weeks.
- **Placebo for 16 weeks followed by secukinumab 300 mg every 2 weeks arm:** subjects receive matching placebo injections.

Thirty-six patients will be randomized per cohort, 24 to active and 12 to placebo treatment, which means that the study will enroll approximately 108 subjects in total.

In Treatment Period 1 all subjects receive weekly subcutaneous injections of blinded study drug (either 300 mg secukinumab or placebo) at weeks 0, 1, 2, 3 and 4. Thereafter the frequency of blinded study drug injections for all subjects is every 4 weeks up to Week 16. Home administration of study drug is **not** allowed during Treatment Period 1. Subjects who complete Treatment Period 1 roll over to Treatment Period 2 at the week 16 visit. The only exception are subjects from the placebo for 16 weeks followed by secukinumab 300 mg every 2 weeks arm,

who achieve spontaneous remission at the Week 16 visit. Spontaneous remission is defined as an IGA of 0 or 1 at Week 16. These subjects do **not** proceed to Treatment Period 2 to avoid unnecessary treatment. Instead they will directly enter the Follow-up Period after the Week 16 visit.

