- Subjects, whether they are willing to continue attending further study visits or not, should attend an End of Treatment (EOT) visit of the study period during which they discontinued (EOT 1 for discontinuation during Treatment Period 1 and EOT 2 for discontinuation during Treatment Period 2). The scheduled visit that was planned to take place will then not be performed and will be replaced by the EOT visit.
- Subjects who are willing to continue will attend visits until Week 16 or Week 32 according to the schedule and will then move to the Follow-up period.
- Subjects who are unwilling to continue attending study visits will move directly to the Follow up period after their EOT visit
- Subjects who discontinue study at the same time as study treatment will end their participation after their EOT visit (see also [Section 9.1.2](#)).

The investigator must also contact the IRT to register the subject's discontinuation from study treatment.

If discontinuation occurs because treatment code has been broken, please refer to [section 6.6.3](#).

If the subject fails to return for EOT assessments for unknown reasons, every effort (e.g. telephone, e-mail, letter) should be made to contact the subject/pre-designated contact as specified in the Lost to Follow-up section. This contact should preferably be done according to the study visit schedule.

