### **9.1.2 Discontinuation of study**

If a subject discontinues study during a treatment period, EOT visit should be performed (see [Section 9.1.1](#) above). If a subject discontinues study during Follow up period, visit Week 40 should be performed.

If the subject cannot or is unwilling to attend any visit(s) after EOT, the site staff should maintain regular telephone contact with the subject, or with a person pre-designated by the subject. This telephone contact should preferably be done according to the study visit schedule.

Documentation of attempts to contact the subject should be recorded in the source documentation.

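### Protocol 10.1.3 gives incompatible end dates for reporting SAEs regardless of causality, and the treatment-emergent and exposure windows do not end together

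*Protocol*

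**What the plan says.** **SAE reporting.** Three statements in Protocol 10.1.3 set an end date.

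- The opening sentence covers every SAE from consent, whatever its suspected cause, "until 30 days [after the last study visit (Week 40) must be reported to Novartis safety within 24 hours".
- Item 2, for randomized or treated subjects, reads "SAEs collected between time subject signs ICF until 10 weeks after the subject has discontinued or stopped study treatment".
- The closing paragraph says that an SAE later than 10 weeks after the last administration "should only be reported to Novartis Safety if the investigator suspects a causal relationship to study treatment".

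Protocol 10.1.1 adds: "Adverse event monitoring should be continued for at least 10 weeks following the last dose of study treatment". It also says that adverse events "must be sought by non-directive questioning of the subject at each visit during the study".

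**Who is still being seen.** Protocol 9.1.1 says: "Subjects who discontinue study at the same time as study treatment will end their participation after their EOT visit". Protocol section 3 places EOT1 four weeks and EOT2 two weeks after the last dose. If a subject will not attend after EOT, Protocol 9.1.2 says that "the site staff should maintain regular telephone contact with the subject". Of placebo subjects in remission at Week 16, Protocol section 3 says: "Instead they will directly enter the Follow-up Period after the Week 16 visit".

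**Analysis windows.** Protocol 12.5.2 closes the treatment-emergent window 84 days after Week 32. SAP 2.7 closes it 84 days after the last dose. SAP 2.1.1.3 and 2.4.1 end exposure at the last visit or 84 days after the last dose, whichever is earlier. SAP 2.7.1 and Table 2-6 plan both a crude incidence and an exposure-adjusted incidence rate for the entire study period. Section 2.7.1 announces a derivation of the rate, but the readable text gives no denominator.

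**The concern.** A site cannot follow both the opening sentence and the closing paragraph of 10.1.3. For an SAE that the investigator does not suspect, whether the 24-hour obligation applies after the 10-week point depends on which sentence the site reads. Sites may differ, so late SAEs would be captured unevenly.

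On the analysis side, the protocol and the SAP would classify the same late event differently, because one window is anchored to a calendar week and the other to the subject's own last dose. Within the SAP, the window for counting events is allowed to run past the day on which exposure stops. If that exposure is the denominator of the exposure-adjusted rate, an event learned of after the last visit, for example by telephone, enters the numerator with no person-time beside it.

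**Working it through.** **Inputs.** Scheduled day = 7 × week + 1. This reproduces the visit table in Protocol Table 8-1: Week 30 = 7 × 30 + 1 = Day 211, Week 32 = Day 225, Week 40 = Day 281. SAP Table 2-3 gives the same days for Weeks 32 and 40. The last injection is at Week 30 in both arms (Protocol 6.1.3). The Protocol glossary counts control drug as study treatment, so a placebo injection is a dose. All days are nominal.

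**Step 1: SAE end dates for a completer.**

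| Statement in Protocol 10.1.3 | Arithmetic | End | Conflict with opening sentence |
|---|---|---|---|
| Opening sentence | 281 + 30 | Day 311 | – |
| Closing paragraph | 211 + 70 | Day 281 | 311 − 281 = 30 days |
| Item 2, treatment stopped = last dose | 211 + 70 | Day 281 | 30 days |
| Item 2, treatment stopped = Week 32 | 225 + 70 | Day 295 | 311 − 295 = 16 days |

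Item 2 allows two readings because Protocol 6.1.4 gives a treatment duration of 32 weeks. The closing paragraph does not: it is anchored to the last administration. The population does not resolve the conflict either. Only randomized subjects reach Week 40, and item 1 gives screen failures their own end date.

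**Step 2: SAE end dates for a subject who leaves at EOT.** If the last study visit means that subject's EOT visit:

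- EOT1: 28 + 30 = last dose + 58 days, against last dose + 70 days.
- EOT2: 14 + 30 = last dose + 44 days, against last dose + 70 days.

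The order reverses, so telling sites to apply whichever rule names the later visit would not be safe.

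**Step 3: treatment-emergent window.**

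- Protocol 12.5.2: 225 + 84 = Day 309 on the nominal calendar.
- SAP 2.7, completer: 211 + 84 = Day 295, which is 14 days earlier.
- SAP 2.7, last dose at Week 4 (Day 29): 29 + 84 = Day 113, which is 309 − 113 = 196 days earlier.

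**Step 4: event window against exposure end, both from the SAP.** Gap = (last dose + 84) − min(last visit, last dose + 84).

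| Route | Last visit | Gap |
|---|---|---|
| Completer | Day 281 = last dose + 70 | 14 days |
| Leaves the study at EOT1 | last dose + 28 | 84 − 28 = 56 days |
| Leaves the study at EOT2 | last dose + 14 | 84 − 14 = 70 days |
| EOT1, then 8-week follow-up | 28 + 56 = last dose + 84 | 0 |
| EOT2, then 8-week follow-up | 14 + 56 = last dose + 70 | 14 days |
| Placebo remitter, last dose Day 85 | 113 + 56 = Day 169 = 85 + 84 | 0 |
| Period 1 stopper seen to Week 16, then follow-up | Day 169; last dose Day 85 or earlier | 0 |
| Period 2 stopper, last dose by Week 28 (Day 197), seen to Week 40 | Day 281; 197 + 84 = 281 | 0 |

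**Step 5: can anything be recorded in the gap?** The 10-week monitoring minimum ends at last dose + 70. That is 70 − 28 = 42 days past EOT1 and 70 − 14 = 56 days past EOT2, so subjects who leave at EOT have monitored days beyond the end of their exposure. For a completer, the minimum ends on Day 281, the same day as the last visit. Days 282 to 295 would then be filled mainly by SAEs reported under the opening sentence of 10.1.3 or the suspected-SAE rule.

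**The case against.** The other side has fair points. The 10-week period appears in item 2, in the closing paragraph and in 10.1.1, while only one sentence uses 30 days. That sentence carries an unclosed bracket, which may point to leftover template text. An experienced site might guess the intended rule. Protocol 10.1.3 also refers to an investigator folder, although it cites it for how to submit rather than for how long. This narrows the conflict but does not remove it: the opening sentence is mandatory as written, and no readable passage overrides it.

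On the rate, parts of the SAP are redacted, so a denominator may be stated where it cannot be read. Completers have almost no route for ordinary adverse events after Day 281, and subjects who withdraw consent may not be contacted further unless safety requires it (Protocol 9.1.3). If last dose meant last active dose, the gap would vanish for Q4W completers (197 + 84 = 281), but it would remain 14 days for Q2W completers, whose last active dose is at Week 30. These points limit the practical effect and make the rate problem conditional.

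Three stronger inferences are tempting, and the documents do not support them.

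- A reader might infer that SAEs suspected to be drug-related could go unreported. They are reportable under every reading.
- A reader might infer that every early stopper has a gap of 56 to 70 days. Those are two separate values, and they apply only to subjects who end participation at EOT1 or EOT2.
- A reader might divide gap days by exposure days and call the ratio the inflation of the rate. That would need a confirmed denominator, complete capture after the last visit, a constant event rate and a dropout rate. The documents give none of these.

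**Conclusion.** The point holds in three parts of unequal strength, and together they should be corrected.

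1. **SAE end date: a contradiction in the text.** For a completer it spans 30 days against the closing paragraph and 30 or 16 days against item 2. It affects only SAEs that the investigator does not suspect. For subjects leaving at EOT, the order of the rules depends on what the last study visit means.
2. **Treatment-emergent window: a mismatch between protocol and SAP.** It is 14 days for completers and much more for early stoppers. It rests only on reading Week 32 in Protocol 12.5.2 as the scheduled week.
3. **Events against person-time: conditional.** The SAP windows differ by 14, 56 or 70 days on the routes shown. This matters for the exposure-adjusted rate only if the exposure of SAP 2.4.1 is its denominator. The effect is then probably small, because little is captured after the last visit, and the documents do not allow a size or a direction between groups to be stated.

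No efficacy endpoint, including IGA response at Week 16, is affected.

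**What to change.** **Protocol 10.1.3.** The sponsor should reconcile the opening sentence, item 2 and the closing paragraph to one end date for SAEs regardless of causality, consistent with the monitoring period in 10.1.1. The text should name the anchor (last administration or a visit) and say how it applies to a subject whose last visit is EOT. Which date to adopt is for the sponsor to decide.

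**Protocol 12.5.2 and SAP 2.7.** Use one anchor and one end date for treatment emergence in both documents.

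**SAP 2.7.1.** State the denominator of the exposure-adjusted rate, and make event counting and person-time stop on the same day. There are two workable ways:

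- End both at a common earlier limit, such as the exposure end of SAP 2.4.1. SAP 5.1.2 already uses the same cap when it imputes AE end dates. The downside is that all later events move to a separate listing: non-serious AEs, and unsuspected as well as suspected SAEs. For subjects leaving at EOT, this includes events in the 42 or 56 days that 10.1.1 still requires to be monitored.
- Extend person-time to the end of AE monitoring and stop counting there. The downside is that person-time is credited for days on which capture may rest on telephone contact alone.

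Either way, the crude incidence in Table 2-6 should use the same set of events, so that the two columns do not describe different data.

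**Cost.** Wording in the protocol (by amendment) and in the SAP, a small programming change and a letter to sites. No visit or assessment is added.
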